5.2 Biomarker study

The case-control study will allow us to evaluate routinely recorded clinical variables, including those constituting existing clinical prediction rules, and current diagnostic tests, such as D-dimer. However, we also plan to evaluate potential alternative biomarkers and undertake more detailed analysis of D-dimer to determine whether a pregnancy-specific threshold could optimise specificity without compromising sensitivity. Patient consent is required to take additional blood samples so the biomarker study will only include women with suspected PE recruited to the prospective study and will not include women with diagnosed PE identified through UKOSS. Since only a small number (~5) will actually have PE, we will augment the sample with pregnant or postpartum women who have DVT diagnosed during the recruitment period at the 8 participating hospitals, thus including all women with diagnosed VTE. There are good pathophysiological reasons for expecting that biomarkers will have the same sensitivity in PE and DVT and empirical studies of D-dimer have shown similar sensitivity in DVT and PE (Stein 2004).

Pregnant or postpartum women with suspected PE recruited to the prospective study will be asked to provide an additional blood sample when blood is taken for routine clinical care. If it is not possible to take the additional sample at the same time as blood sampling for routine care the patient will be asked to provide an additional blood sample, which may require the patient to undergo an additional venepuncture procedure. In addition, we will recruit any women with a DVT diagnosis confirmed by imaging (ultrasound, magnetic resonance, CT or contrast venography) who is willing to provide an additional blood sample. The incidence of DVT in pregnancy and postpartum is around 4 times that of PE (Kane 2013) so we anticipate recruiting around 20 women with DVT. Thus the sample for the biomarker sub-study will include 245 women with suspected PE but negative diagnostic testing, 5 women with diagnosed PE and 20 women with diagnosed DVT (i.e. 25 with VTE).

Blood samples will be stored and transported for analysis at Guys and St Thomas's (GSTT) Hospital. Analysis will involve (1) comparison of biomarker levels between women with and without thromboembolism, (2) construction of receiving operator characteristic (ROC) curves and calculation of the area under ROC curve, and (3) exploration of the impact of using a pregnancy-specific threshold upon the ROC analysis.

We plan to test the following biomarkers (see Table 4), along with any potential new biomarkers that become available during the project

Table 4: Biomarkers to be tested

Biomarker	Description
D-Dimers (ELISA)	A fibrin degradation product - a small protein fragment
	present in the blood after a blood clot is degraded by
	fibrinolysis. Measured by enzyme-linked immunoassay
	(ELISA) and a highly sensitive assay.
D-dimers (latex	As above, but measured by latex agglutination. This is a
agglutination)	point of care test that is used by many routine
	laboratories
Plasmin-antiplasmin assay	An ELISA assay that measures the level of plasmin-
(PAP)	antiplasmin complexes and thus is a very sensitive assay
	of plasmin activation.
Prothrombin fragment 1+2	A small molecule cleaved from prothrombin when
(PF 1 +2)	thrombin is generated. It is thus a sensitive marker of

	thrombin generation i.e. coagulation turnover. It is an ELISA assay
Thrombin Generation	Thrombin generation can be measured dynamically using the Endogenous Thrombin Potential [ETP], a term introduced by Hemker in 1986 that refers to the total amount of thrombin generated during the test. Commonly measured variables when analysing thrombin generation include the Lag Time, the Time to Peak Thrombin Generation, the Endogenous Thrombin Potential [ETP] - the area under the curve.
Prothrombin time (PT)	A routine measure of the extrinsic pathway of coagulation, used to determine the clotting tendency of blood.
Activated partial thromboplastin time (APTT)	A routine measure of the intrinsic and common coagulation pathways, used to detect abnormalities in blood clotting.
Clauss Fibrinogen	A functional measure of fibrinogen
Soluble Tissue Factor (sTF)	A marker of tissue factor activation - when tissue factor is upregulated part of the molecule enters the systemic circulation.
Troponin I	Part of the troponin complex in cardiac muscle tissue, used to detect myocardial damage resulting from myocardial ischaemia or noncardiac causes such as PE.
B-type natriuretic peptide	A polypeptide secreted by the ventricles of the heart in response to excessive stretching of heart muscle cells, used to measure heart strain resulting from primary heart disease or noncardiac causes such as PE.
C- Reactive Protein (CRP)	CRP is an acute-phase protein, the levels of which rise in response to inflammation. Elevation of CRP has been shown to be associated with a diagnosis of PE.

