5.3 Decision-analysis modelling

Decision-analysis modelling will be used to estimate costs incurred and expected outcomes from thromboembolism, bleeding and radiation exposure if a hypothetical cohort of pregnant or postpartum women were investigated for suspected PE using different strategies. These will include a no imaging strategy (i.e. no treatment), imaging for all, and a range of strategies with varying sensitivity and specificity in which women are selected for imaging on the basis of clinical characteristics, a clinical prediction rule or biomarker measurement. The sensitivity and specificity of these strategies will be estimated using our primary data. Sensitivities of strategies based on clinical predictors will be estimated from the ~150 cases with diagnosed PE. Sensitivities of biomarker strategies will be estimated from the ~25 women with PE or DVT included in the biomarker study. Specificities of all strategies will be estimated from the ~245 women with suspected PE who have negative diagnostic imaging.

Each diagnostic strategy will be applied to the hypothetical cohort to estimate the number of true and false positives and negatives based upon our estimates of sensitivity and specificity. We will assume that true and false positives undergo imaging while true and false negatives are discharged without treatment. Estimates of the diagnostic accuracy of imaging (NICE, 2012) will be used to determine whether imaging results in appropriate treatment of PE or inappropriate treatment of women without PE. We will use methods developed in our evidence synthesis of diagnostic

testing for DVT (Goodacre 2006, Bates 2012) to estimate the effect of treatment for PE and existing meta-analysis to estimate risks of recurrent fatal and non-fatal PE with anticoagulation, and risks of haemorrhage with anticoagulation (Carrier 2010, Linkins 1998, Douketis 2003).

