Biomarker strategies will be tested using data from the biomarker study, although this analysis will inevitably be limited by the data available. Biomarkers will be selected for analysis if accuracy data suggest diagnostic value (i.e. a c-statistic significantly better than 0.5 and at least comparable to D-dimer). We will model the cost-effectiveness of each biomarker (compared to no imaging, imaging for all and imaging based on clinical predictors) at varying thresholds for positivity to estimate the optimal threshold. Sensitivity analyses will be used to explore the potential impact of uncertainty in estimates of biomarker diagnostic sensitivity, in terms of imprecision (due to the small number with VTE in the primary data), inaccuracy (due to the need to extrapolate data from VTE to those with PE) and "statistical shrinkage" (due to the use of an unvalidated data-derived threshold for positivity).

Value of information analyses will be conducted to determine the overall gain associated with: removing all uncertainty from the decision problem (Expected Value of Perfect Information); removing all uncertainty from a subset of parameters (Expected Value of Partial Perfect Information); and if these values are sufficiently large, the expected value of conducting future research assuming finite sized trials (Expected Value of Sample Information). The exact focus of such analyses would be determined during the research but candidate studies would include a prospective cohort study and

the collection of further evidence to validate the adoption decision advocated by current evidence.

We will specifically use value of information analysis to explore the value of undertaking a prospective study to obtain more accurate, precise and prospectively validated estimates of diagnostic sensitivity for a clinical prediction rule or biomarker.

6. Statistics

Sample size

Data will be collected from 150 UKOSS cases with diagnosed PE and up to 325 pregnant or postpartum women with suspected PE, resulting in about 156 cases with PE and 321 controls without, assuming prevalence of PE is 2% in those with suspected PE. Potential attrition in the primary outcome data of up to 25% in the suspected PE group will allow for a sample size of 250 women with complete Suspected PE data and achieve an estimation of sensitivity or specificity of 90% with a standard error of about 2.5% and 2.0% respectively.

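### Pooling about 20 DVT women with about 5 PE women rests on an equal-sensitivity assumption that Table 4 does not support for troponin I and BNP, so a cardiac marker informative for PE could be screened out

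*Protocol*

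**What the plan says.** Protocol Section 5.2 explains the pooling: "Since only a small number (~5) will actually have PE, we will augment the sample with pregnant or postpartum women who have DVT". DVT incidence is put at "around 4 times that of PE (Kane 2013) so we anticipate recruiting around 20 women with DVT". The planned sample is 245 test-negative women, 5 with PE and 20 with DVT. The justification is "There are good pathophysiological reasons for expecting that biomarkers will have the same sensitivity in PE and DVT". Section 3.2 makes the same argument in a slightly weaker form, claiming similar sensitivity for the candidate biomarkers. Neither section excepts any marker, and both cite empirical evidence for D-dimer only.

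Table 4 has twelve entries. Troponin I is "used to detect myocardial damage resulting from myocardial ischaemia or noncardiac causes such as PE". BNP is "used to measure heart strain resulting from primary heart disease or noncardiac causes such as PE". In Section 4, the exclusion criteria for the Diagnosed DVT group remove women with suspected PE, who go to the suspected PE group instead.

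The first analysis listed in Section 5.2 compares marker levels in women with and without thromboembolism. For the decision model, Section 5.3 states: "Sensitivities of biomarker strategies will be estimated from the ~25 women with PE or DVT included in the biomarker study". A marker is taken into the model only if it shows "a c-statistic significantly better than 0.5 and at least comparable to D-dimer". For markers that are modelled, Section 5.3 plans sensitivity analyses, one of which covers the inaccuracy of carrying VTE results over to PE.

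**The concern.** A shared mechanism in PE and DVT is a reasonable argument for markers of clotting and fibrinolysis. It does not carry over to troponin I and BNP, because the route Table 4 describes for them runs through the heart. The DVT group is recruited without suspected PE, so there is no stated reason to expect these two markers to be raised there as often as in PE.

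The target condition is PE: the study aims to select women with suspected PE for imaging, and the model applies the estimated sensitivities to a suspected-PE cohort. If four in five cases come from a condition in which a cardiac marker may be little raised, its reported sensitivity and c-statistic are pulled towards the DVT values. The planned check on extrapolating from VTE to PE does not protect the selection step, because it applies only to markers already chosen for modelling. Nor does it protect the reported ROC results.

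**Working it through.** **Reproducing the plan's counts.** 2% of 250 = 5 PE; 98% of 250 = 245 negative; 4 × 5 = 20 DVT; 5 + 20 = 25 VTE. The counts are sound. The DVT share is 20/25 = 80%. With the updated figure of about 6 PE in Section 3.2, it is 24/30 = 80% at the same 4:1 ratio, or 20/26 = 77% if DVT recruitment stays at 20.

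**Formulas.** For a mixture of case types against the same controls:
- pooled c-statistic = 0.2 × c(PE) + 0.8 × c(DVT)
- pooled sensitivity = 0.2 × Se(PE) + 0.8 × Se(DVT)
- null SE of the c-statistic = √[(n1 + n0 + 1)/(12 × n1 × n0)]
- chance of significance ≈ Φ[(pooled c − 0.5)/SE − 1.96]

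For 25 v 245, null SE = √[271/(12 × 25 × 245)] = 0.061.

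**C-statistic.** The protocol gives no c-statistics for these markers, so all values below are assumptions.

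| c(PE) | c(DVT) | Pooled c | Chance significantly above 0.5 |
|---|---|---|---|
| 0.80 | 0.50 | 0.56 | about 17% |
| 0.80 | 0.60 | 0.64 | about 64% |
| 0.90 | 0.50 | 0.58 | about 25–27% |
| 1.00 | 0.50 | 0.60 | about 35–38% |
| 0.70 | 0.60 | 0.62 | about 51% |
| 1.00 | 0.60 | 0.68 | about 84% |

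First row: 0.2 × 0.80 + 0.8 × 0.50 = 0.56; 0.06/0.0607 = 0.99; Φ(0.99 − 1.96) = 0.17. Second row: 0.2 × 0.80 + 0.8 × 0.60 = 0.64; 0.14/0.0607 = 2.31; Φ(2.31 − 1.96) = 0.64. Where a range is shown, the lower figure is from a simulation with a normal shift in PE women only (4,000 runs; the c(PE) = 1.00 row was simulated at 0.999). That simulation gave 16% for the first row.

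**Is the loss due to dilution or to small numbers?** In the same simulation, an analysis of 5 PE v 245 reached significance in 71% of runs at c(PE) = 0.80 and 97% at 0.90. The pooled analysis reached 16% and 25%. When c(DVT) is 0.50, adding the DVT women therefore lowers the chance of detecting a PE marker.

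**Sensitivity.** Again with assumed values:
- Se(PE) 40%, DVT positivity 5%: 0.2 × 0.40 + 0.8 × 0.05 = 12%.
- Se(PE) 30–50%, DVT positivity 3–10%: pooled 8% to 18%.
- Se(PE) 95%, DVT positivity 5–10%: pooled 23% to 27%.

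**Precision of a PE-only analysis.** Null SE of the c-statistic = √[251/(12 × 5 × 245)] = 0.13 with 5 PE cases, and √[252/(12 × 6 × 245)] = 0.12 with 6. A true sensitivity of 90% has SE √(0.09/5) = 13.4 points with 5 cases, against √(0.09/25) = 6.0 points with 25. If all 5 were positive, the exact 95% lower limit would be 48%.

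**The case against.** Several points on the other side stand.

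- A reader might infer that equal sensitivity cannot hold for troponin I and BNP. The protocol does not go that far: Table 4 names PE as an example, not as the only noncardiac cause. Nor do the DVT women have no possible route through PE, since only suspected PE is excluded and some may have unsuspected PE.
- A reader might infer that a useful cardiac marker would be rejected. That depends on a DVT c-statistic of 0.50, which the protocol does not supply. At 0.60, with 0.80 in PE, the chance of passing the significance part of the rule is about 64%.
- Section 5.3 does not say which case group its c-statistic uses. Pooling is the likeliest reading, given the thromboembolism comparison in Section 5.2 and the roughly 25 women used for sensitivity, but it is an inference.
- The prospective women may not be the only PE data. Section 5.1.1 asks UKOSS clinicians to record other biomarkers done in routine care, and Section 6 plans biomarker accuracy estimates from cases and controls. However, Section 5.2 keeps UKOSS women out of the biomarker study, and the completeness of routine results is unknown.
- The objective is exploratory, and Section 5.3 concedes that the data are limited. Separate PE and DVT tables may be in the SAP, which is not at hand.
- A marker with 30–50% sensitivity for PE would have little value for ruling it out, so reporting 12% instead of 40% might change nothing. The calculation at 95% sensitivity shows that the same dilution would hide a marker that did matter.

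These points limit the wording and the severity. They do not supply a reason for applying a D-dimer rationale to the cardiac markers, and they do not protect the selection step.

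**Conclusion.** The concern holds in limited form. The blanket assumption in Sections 3.2 and 5.2 is unsupported by Table 4, and implausible under it, for two of its twelve entries. DVT women make up about 80% of the VTE cases, so the pooled sensitivity for troponin I and BNP would mostly describe DVT. So would the selection c-statistic if it is pooled. A marker informative for PE could then fail the rule before the planned extrapolation analysis is reached. The size depends on unknown performance in DVT: for a PE c-statistic of 0.80, the chance of significance runs from about 17% (DVT 0.50) to about 64% (DVT 0.60). This should be fixed, but it is not critical: the work is exploratory, and the clinical-predictor and prediction-rule objectives are unaffected.

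**What to change.** 1. In Sections 3.2 and 5.2, limit the equal-sensitivity rationale to markers of clot formation and breakdown.
2. For troponin I and BNP, estimate the c-statistic and sensitivity against PE only and label them descriptive.
3. In Section 5.3, state which case group the selection c-statistic uses, and do not use a pooled VTE c-statistic to reject these two markers. If they are modelled, do so only as an exploratory scenario that carries the PE-only estimate with its full uncertainty.
4. For every other marker, including CRP, show PE and DVT results separately beside the pooled figure.
5. Any troponin or BNP results recorded for UKOSS cases in routine care may be described as supporting PE data, with their completeness stated.

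The cost is some wording and one stratified table, using data already planned for collection. The downside is imprecision: with about 5 to 6 prospective PE cases, no firm conclusion on the cardiac markers is possible, and the report should say so.

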5.3 Decision-analysis modelling

Decision-analysis modelling will be used to estimate costs incurred and expected outcomes from thromboembolism, bleeding and radiation exposure if a hypothetical cohort of pregnant or postpartum women were investigated for suspected PE using different strategies. These will include a no imaging strategy (i.e. no treatment), imaging for all, and a range of strategies with varying sensitivity and specificity in which women are selected for imaging on the basis of clinical characteristics, a clinical prediction rule or biomarker measurement. The sensitivity and specificity of these strategies will be estimated using our primary data. Sensitivities of strategies based on clinical predictors will be estimated from the ~150 cases with diagnosed PE. Sensitivities of biomarker strategies will be estimated from the ~25 women with PE or DVT included in the biomarker study. Specificities of all strategies will be estimated from the ~245 women with suspected PE who have negative diagnostic imaging.

Each diagnostic strategy will be applied to the hypothetical cohort to estimate the number of true and false positives and negatives based upon our estimates of sensitivity and specificity. We will assume that true and false positives undergo imaging while true and false negatives are discharged without treatment. Estimates of the diagnostic accuracy of imaging (NICE, 2012) will be used to determine whether imaging results in appropriate treatment of PE or inappropriate treatment of women without PE. We will use methods developed in our evidence synthesis of diagnostic

testing for DVT (Goodacre 2006, Bates 2012) to estimate the effect of treatment for PE and existing meta-analysis to estimate risks of recurrent fatal and non-fatal PE with anticoagulation, and risks of haemorrhage with anticoagulation (Carrier 2010, Linkins 1998, Douketis 2003).

Outcomes will be modelled to estimate the quality-adjusted life years (QALYs) accrued by each strategy. Existing data sources and our previous evidence synthesis projects (Goodacre 2006) will be used to estimate QALYs after PE and complications of treatment, and estimate a QALY loss for diagnostic imaging based on the risk of radiation-related malignancy. Costs for initial hospital assessment, diagnostic testing, treatment of PE and treatment of complications will be estimated using NHS reference costs. The incremental cost per QALY gained by each strategy compared to the next most effective alternative on the efficiency frontier will determine the adoption strategy at current NICE thresholds. The precise modelling methodology will be determined as the model is developed in the project. This decision will be made in conjunction with clinical experts and having assessed the available data. The research team are highly familiar with cohort Markov models and decision trees, and have published using more advanced methods such as individual patient modelling (Stevenson 2005), discrete event simulation (Stevenson 2010 a), area under the curve analyses (Stevenson 2010b) and meta-modelling (Stevenson 2004).

We will undertake sensitivity analysis, guided by input from an expert clinical group, to test key assumptions in the model, such as the assumed sensitivity and specificity of diagnostic imaging, the effect of treating PE (especially subsegmental PE), the effect of using CTPA or VQ scanning as the imaging method, and inaccuracy and imprecision in estimates of strategy diagnostic accuracy.

We will specifically undertake a sensitivity analysis to explore the effect of any potential design-related bias upon our estimates of diagnostic sensitivity. Lijmer *et al* (1999) estimated the effect of design-related bias in diagnostic accuracy studies. Use of a case-control design appears to overestimate the diagnostic odds ratio compared to a cohort design, although this may be more relevant to studies that use a control group from the normal population rather than symptomatic controls presenting with suspected disease (as with our primary data). Nevertheless, we will use this estimate to adjust our estimates of diagnostic sensitivity to explore the potential impact of design-related bias.

Biomarker strategies will be tested using data from the biomarker study, although this analysis will inevitably be limited by the data available. Biomarkers will be selected for analysis if accuracy data suggest diagnostic value (i.e. a c-statistic significantly better than 0.5 and at least comparable to D-dimer). We will model the cost-effectiveness of each biomarker (compared to no imaging, imaging for all and imaging based on clinical predictors) at varying thresholds for positivity to estimate the optimal threshold. Sensitivity analyses will be used to explore the potential impact of uncertainty in estimates of biomarker diagnostic sensitivity, in terms of imprecision (due to the small number with VTE in the primary data), inaccuracy (due to the need to extrapolate data from VTE to those with PE) and "statistical shrinkage" (due to the use of an unvalidated data-derived threshold for positivity).

Value of information analyses will be conducted to determine the overall gain associated with: removing all uncertainty from the decision problem (Expected Value of Perfect Information); removing all uncertainty from a subset of parameters (Expected Value of Partial Perfect Information); and if these values are sufficiently large, the expected value of conducting future research assuming finite sized trials (Expected Value of Sample Information). The exact focus of such analyses would be determined during the research but candidate studies would include a prospective cohort study and

the collection of further evidence to validate the adoption decision advocated by current evidence.

We will specifically use value of information analysis to explore the value of undertaking a prospective study to obtain more accurate, precise and prospectively validated estimates of diagnostic sensitivity for a clinical prediction rule or biomarker.

6. Statistics

Sample size

Data will be collected from 150 UKOSS cases with diagnosed PE and up to 325 pregnant or postpartum women with suspected PE, resulting in about 156 cases with PE and 321 controls without, assuming prevalence of PE is 2% in those with suspected PE. Potential attrition in the primary outcome data of up to 25% in the suspected PE group will allow for a sample size of 250 women with complete Suspected PE data and achieve an estimation of sensitivity or specificity of 90% with a standard error of about 2.5% and 2.0% respectively.

If we assume that the ratio of cases to controls is about 0.4, then this sample size is sufficient to identify an odds ratio of a clinical predictor of about 2, with 90% power and 5% two sided significance (Machin 2009).

Data Analysis

Women with PE who did not present with suspected PE prior to diagnosis, i.e. those who need life support upon presentation to hospital (including chest compressions and ventilator support) will be excluded from primary and secondary analyses, but their data used to estimate key parameters, such as incidence of PE in pregnancy and postpartum.

Two independent assessors, blind to clinical predictors and blood results, will classify participants as having PE using diagnostic imaging results, details of adverse events and details of treatments given. Disagreements will be resolved through adjudication by a third assessor. Women with a clinical diagnosis of PE based on imaging evidence of DVT will be analysed as cases. Women with a purely clinical diagnosis of PE (i.e. without any imaging evidence of DVT or PE) will be excluded from primary analysis but included as cases in secondary analysis. Women with clinically ruled out PE (i.e. suspected PE without diagnostic imaging for PE) will be excluded from the primary analysis but included as controls in secondary analysis.

Women with multiple presentations i.e. classified as having a PE in the Suspected PE group and also identified through UKOSS, will be cross referenced using the date of the PE and the woman's year of birth to ensure that case is only used once in the analysis. Similarly, for the biomarker study, women collected as a Diagnosed DVT and then also included as a Suspected PE will also cross referenced and their blood samples will be highlighted as being from the same individual.

Sensitivity, specificity, likelihood ratios and/or c-statistics will be estimated with a 95% confidence interval for clinical predictors, biomarkers and existing prediction rules (Wells, Geneva and PERC) using data from cases and controls. Chi-square or Fisher's Exact tests will be used to test the association between PE diagnosis and each clinical variables, D-dimer (dichotomised at the standard threshold) and prediction rule. Multivariate analysis will then be used to identify which variables are independent predictors of PE. If the multivariate model suggests that a new combination of variables

or a modified rule could outperform existing rules we will develop a new rule from the model variables or modify an existing rule with the aim of achieving the highest specificity at which sensitivity of at least 95% is maintained. The multivariate model will be validated internally using cross-validation, i.e. the data will be split into a training and validation set at random, in the ratio 2:1 and the model fit to the training and tested in the validation test. In addition we will use bootstrapping to validate the model (Royston 2009).

Secondary analyses will explore (a) whether the findings differ between pregnant and postpartum women, and (b) whether findings are sensitive to the inclusion of women with clinically diagnosed PE in the reference standard definition. An additional secondary analysis will test the performance of a clinical decision rule developed through expert consensus. Standard Delphi and Nominal Group methodology will be used with panel membership including obstetric, emergency medicine, haematology, and radiology expertise (Dalkey 1972, Delbecq and Van de Ven 1971). The sensitivity and specificity of the resulting CDR for identifying diagnosed PE will then be determined in the DiPEP cohort.

Further details will be provided in a separate statistical analysis plan.

7. Study supervision

A Steering Committee will be appointed to provide independent oversight. It will consist of SG, the project manager, two patient/public representatives ([name] and [name]) and four independent experts, one of whom will chair the committee.

The study will be managed by a full-time project manager based in the Sheffield CTRU. The CTRU will also provide data management, statistical and health economic support. A Project Management Group consisting of the co-applicants and appointed research staff will undertake day to day management of the study and will meet at least quarterly.

The study Sponsor will be Sheffield Teaching Hospitals NHS Foundation Trust and SG will take overall responsibility for the study.

There will be no Data Monitoring and Ethics Committee (DMEC) required for this study. A data management and monitoring plan will be devised in accordance with the Sheffield CTRU SOP (DM009)

Subcontracts will be drawn up between the University of Sheffield and other participating institutions. [name] from the National Perinatal Epidemiology Unit will be responsible for the UKOSS research platform to identify cases of diagnosed PE. [name] from Guy's and St Thomas's Hospital will be responsible for the biomarker analysis.

8. Plan of investigation and timetable

The project will take 30 months to complete and will involve three phases:

Phase 1 will take six months (1/10/14-31/3/15) and involve obtaining ethics and R&D approval, setting up the project across participating sites, updating the literature review and finalising data collection.

Phase 2 will take 18 months (1/4/15-30/9/16) and involve primary data collection for cases (UKOSS, all UK hospitals commencing 1/4/15) and controls (11 hospitals, staggered start from 1/4/15 to 30/9/15), and development of the decision-analysis model.

Phase 3 will take six months (1/10/16-31/3/17) and involve follow-up, analysis, incorporation of primary data into the model and writing-up.

Progress reports will be submitted 6-monthly:

- 1. 31/3/15: Details of approvals, finalised protocol and data collection
- 2. 30/9/15: Identification of diagnosed PE started from the UKOSS research platform (target=50) and recruitment of suspected PE started at all eleven hospitals (target=50)
- 3. 31/3/16: Progress on identification of diagnosed PE (target=100) and recruitment of suspected PE (target=150)
- 4. 30/9/16: Progress on identification of diagnosed PE (target=150) and recruitment of suspected PE (target=325)

9. Data handling and record keeping

Participant confidentiality will be respected at all times during the DiPEP project. Data will be collected and handled in line with CTRU Standard Operating Procedures and in accordance with NHS Trust policies at Sheffield Teaching Hospitals NHS Foundation Trust and at each participating site. This will ensure systems are in place to protect confidentiality of participants and the systems are secure.

The UKOSS research platform will not collect names, addresses, postcodes, dates of birth, NHS or hospital numbers. Women with diagnosed PE will be identified by a member of the clinical care team who will extract anonymised data from the hospital records. Data will be recorded on a case report form with a unique study number but no personal details. For UKOSS cases, the case report form will be mailed to UKOSS at the National Perinatal Epidemiology Unit at the University of Oxford. Data will be entered onto a secure password protected electronic database within UKOSS. The database will then be emailed to Sheffield CTRU with the password mailed separately. The paper case report forms will be destroyed when data entry and data checking is complete.

For women with suspected PE, data will be entered onto a secure online database by a clinical research nurse employed by the hospital. A separate database held within the hospital by the principal investigator or research nurse will link the unique study number to the patient's hospital number to allow audit, avoid duplication and avoid repeated requests to participate resulting from multiple admissions. Patient name, telephone number, email and/or address will be entered onto the secure online database for women consenting to questionnaire follow-up. These details will be recorded on the case report form but will be blacked out on the paper form when they are entered onto the online database.

Bloods samples from women with suspected PE will be will be identified by unique study identifier only. This will allow us to link to the patient records for purposes of audit and monitoring. The researchers analysing the blood samples at GSTT will not have access to personal details and blood results will not be made available to anyone associated with the patient or involved in their care.

All consent forms, CRFs, questionnaires will be kept in a locked filing cabinet in a secured area and will be destroyed at least 5 years after study completion. The consent forms will be kept in a separate place to the CRFs and questionnaires so that none of the data will be identifiable.

10. Data access and quality assurance

For the UKOSS research platform, the security of all data will be maintained by storage on a secure University network, accessible only by the key researchers and responsible members of the University of Oxford who may require access to data to ensure compliance with regulations. Access by any other individuals for the purposes of any other study will only be allowed after review by the UK Obstetric Surveillance System Steering Committee and further reference to a Research Ethics Committee.

For the suspected PE part of this study, the study manager, research assistant and data managers based at Sheffield CTRU will have access to the anonymised data on the database through the use of usernames and encrypted passwords. Select CTRU staff will have access to personal data including names, addresses, phone numbers and email addresses in order to undertake the questionnaire follow-up. In addition to this, access to hard copies of the CRF and questionnaire data will be required for study monitoring and audit purposes. A study monitoring plan will be devised in accordance with the Sheffield CTRU SOPs on Trial Monitoring (QU001) and Data management and monitoring plan (DM009).

The study database resides on Sheffield CTRU's in house data management system. The system uses industry standard techniques to provide security, including password authentication and encryption using SSL/TLS. Access to the system is controlled by usernames and encrypted passwords, and a comprehensive privilege management feature can be used to ensure that users have access to only the minimum amount of data required to complete their tasks. This will be used to restrict access to personal identifiable data. The secure data management system will incorporate quality control procedures to validate the study data. Error reports will be generated where data clarification is required.

11. Publication

We have strong links with guideline development groups and our previous research has influenced a number of national and international guidelines. Our previous HTA-funded evidence synthesis on diagnostic testing for DVT (Goodacre 2006) formed the basis of NICE guidance (NICE 2012) and American College of Chest Physicians Evidence-Based Clinical Practice Guidelines for DVT diagnosis (Bates 2012).

Indiscriminate use of diagnostic imaging for women with suspected PE in pregnancy is unsurprising given the lack of evidence that any clinical predictor, rule or biomarker can rule-out PE in this patient group. This study will be the first to provide reasonably precise estimates of the sensitivity of clinical assessments. If it shows that a clinical predictor, rule or biomarker can rule-out PE then this will for the first time provide clinicians and guideline-developers evidence that a simple diagnostic strategy can safely reduce the use of imaging and associated health care costs.

It is entirely possible that this study will show that an existing clinical prediction rule and/or the use of D-dimer at an appropriate threshold can rule-out PE and achieve sufficient specificity to allow a substantial proportion of women to avoid imaging. If not, our data will allow us to modify existing rules or develop a new rule with greater sensitivity and specificity. Any new rule would need validation in a new study. We will determine whether a prospective cohort study is feasible, and whether such a study would represent value for money.

Estimation of biomarker levels in women with suspected PE but negative testing will help clinicians to interpret blood test data and identify which biomarkers may be diagnostically useful in pregnancy. Normal ranges for biomarkers are currently based on non-pregnant populations and even when they have been measured in pregnant patients these are not patients with symptoms suggestive of PE.

Decision-analysis modelling will provide estimates of the relative benefits, harms and costs of testing for suspected PE in pregnant and postpartum women with varying risk of PE. These findings will help clinicians to make individualised decisions about the use of imaging and potentially allow informed patient involvement in decision-making. We will specifically identify the threshold of risk of PE at which the benefits of imaging outweigh the harms and the threshold at which the benefit justifies the costs.

We will disseminate our findings in the following ways:

